## 2 STUDY OBJECTIVES

The purpose of this study is to determine whether the use of virtual reality after pediatric idiopathic scoliosis surgery influences pain perception. We hypothesize that the use of virtual reality programs will provide superior distraction to standard electronic use and will result in improved pain scores and reduced opioid consumption after surgery.

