Both iPads and VR devices are interactive (regardless of fingers versus head movement) and this type of movement difference should not confound results. Our study aims to assess whether the VR immersive experience provides superior distraction to the standard of care (iPad use), thus by nature of the study design we are studying the difference in the two distinct types of experiences. Finger versus head movement use is inherent to the types of distraction and central to the distinct experiences. Similarly, there will be different apps between VR and iPad platforms by nature of the differences in platforms. Our goal is to examine whether an immersive experience is more beneficial than an iPad-based experience, rather than examine specific styles of games.

There will be no restriction to personal electronic use. Both groups will have access to their personal devices (cell phones, iPads) as is the standard of care. The study iPad will only be offered at specific times as designated twice a day on POD#1 for participants in the control group. Outside of the study windows, participants will not be provided with hospital iPads. Personal electronic devices including iPads are acceptable, as is the standard of care for patients to bring whatever they see fit into the hospital.

There will be a variety of popular games and apps, deemed to be content- and age-appropriate by the Child Life specialists. Program offerings will not vary by specific age or gender; our study will only include ages 11-17 and per discussion with Child Life the programs do not need to be subdivided to remain appropriate within this age range.

Standard of care for both groups will include PCA use as ordered by the surgical team as well as routine Child Life visits. The Child Life team is an integral part of pediatric postoperative recovery at UNC.

The following will be recorded: Number of hours since anesthesia end. Pain scores including FACES scale by the patient and FLACC scores by the research assistant will be recorded immediately prior to intervention (T=0) and at end of intervention (T=30); FLACC score will also be recorded at the 10 minute mark (T=10). PCA use, in mcg or mg as appropriate, for the hour prior to intervention (T=-60-0), during intervention (T=0-30), and one hour after intervention is complete (T=30-90) will be recorded. Total number of minutes of electronic device use will be recorded. PCA use will be converted to morphine equivalents at time of data entry.

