The anesthetic management of the patients will be left to the discretion of the anesthesia provider on the day of surgery but will follow the guiding principles of the pediatric spine ERAS protocol, which standardizes many aspects of anesthetic care including multimodal analgesia, fluid management, etc.

We are limiting our scope to POD#1 opioid usage. We do not hypothesize that VR use on POD#1 will affect opioid usage following hospital discharge.

Follow up: A follow up survey will be given using the Post Hospitalization Behavior Questionnaire for Ambulatory Surgery (PHBQ-AS) form at approximately 48-72 hours postop and 7-10 days postop via a phone call, email or in person from a member of the research team. The PHBQ-AS form is used to assess new onset behavior change associated with hospitalization, which has been documented in numerous studies. We believe that by assessing preoperative anxiety and preventing perioperative pain, which can lead to behavioral changes, the use of VR may decrease the chance of post hospitalization behavior change.

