## 4.2 Intervention/Treatment procedures (by visits)

There will be two intervention/treatment visits, both occurring on POD#1. On POD#1 in the morning, patients in both groups will be visited by the research assistant. Patients in the VR arm will be offered the VR device for up to 30 minutes. Patients in the control arm will be offered an iPad for up to 30 minutes. After a total of 30 minutes maximum, the session will end. Routine data will be collected on pain scores and PCA use as above for both groups. On POD #1 in the afternoon, a research assistant will return for patients in both groups. For participants in the intervention group, this VR session will be again offered for up to 30 minutes. Patients in the control arm will be offered an iPad for up to 30 minutes. If a patient declines to participate, the reason for declining will be asked for and recorded.

To evaluate efficacy, the following will be recorded:

- Primary outcomes:
  - Postoperative pain scores
  - Postoperative PCA opioid use surrounding intervention (morphine equivalents)
- Secondary outcomes:
  - Patient and caregiver satisfaction scores
  - Presence of dizziness/nausea
  - Time of discontinuation of VR if less than 30 minutes

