#### 4.5 Concomitant Medication documentation

PCA opioid use surrounding intervention (morphine equivalents), at time intervals as detailed above, will be recorded. Any anti-nausea medication requested during the intervention will be recorded. Given that our study will take place on POD#1, perioperative medications given intra-operatively will not be included for analysis.

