## 5.3 Safety Evaluations

Safety and feasibility of VR in postsurgical populations has been proven in previous studies, some of which include specific spine surgery populations. As we are limiting the use of the virtual reality headset to 30 minutes, there is a possibility that patients may experience anxiety and/or notice an increase in pain following cessation of VR. As such, the patients will be permitted to freely use personal electronic devices without restriction, which is the standard of care at present. We feel that by doing this, the chance of anxiety related to complete withdrawal of electronic distraction will be low, as will

the possibility of any adverse effects such as nausea or dizziness. The incidence of dizziness and nausea with the use of virtual reality is not precisely known and is not agreed upon in the literature. As it is mentioned in various studies as a potential side effect, we will limit the use of the virtual reality headsets to 30 minutes to minimize the risk.

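### PCA use is recorded only around two sessions, so the opioid endpoint supports a peri-session claim but not one about postoperative or POD#1 opioid consumption

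*Combined protocol and SAP*

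**What the plan says.** Section 2 predicts that VR "will result in improved pain scores and reduced opioid consumption after surgery". The primary objective (2.1) and Aim 2 (6.3) are likewise about postoperative opioid use, with no time window attached. In the study phases of section 3.1 the plan adds: "We are limiting our scope to POD#1 opioid usage". The next sentence says that no effect on use after discharge is expected.

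The outcome is defined more narrowly. Section 4.2 lists "Postoperative PCA opioid use surrounding intervention (morphine equivalents" as a primary outcome, and the synopsis and section 6.1 use the same limitation. Sections 3.1 and 5 set the intervals: the hour before the session, then "during intervention (T=0-30), and one hour after intervention is complete (T=30-90) will be recorded". Section 4.2 states: "There will be two intervention/treatment visits, both occurring on POD#1". Section 4.5 confines opioid recording to the same intervals: "PCA opioid use surrounding intervention (morphine equivalents), at time intervals as detailed above, will be recorded". The chart-abstraction list in section 5 contains no POD#1 opioid total.

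Section 6.3 compares opioid consumption between arms with a two-sample t-test. It does not say which windows enter, how the two sessions are combined, or whether the pre-session hour is a baseline. Section 5.3 notes that "there is a possibility that patients may experience anxiety and/or notice an increase in pain following cessation of VR".

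**The concern.** PCA is self-administered, so a distracted patient may need less opioid or may simply press later. An outcome that stops counting at T=90 gives the same result in both cases if the later presses fall outside the recorded windows. The objective and hypothesis are about the amount consumed, and the rationale in section 1.3 is that children may receive fewer opioids with fewer adverse effects. That benefit depends on the amount, not on when in the day it is taken.

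Two uses of the result are exposed. The synopsis says that postoperative management protocols may be modified in light of the findings. Section 6.4 says that the pilot will supply the effect size for the primary outcome. A windowed difference read as a reduction in postoperative opioid use would mislead both.

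**Working it through.** The plan gives no effect size, SD or power for the opioid endpoint, so there is no stated figure to reproduce.

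**Inputs from the documents.** Windows of 60, 30 and 60 minutes (sections 3.1 and 5); two sessions (4.2); 10 completers per arm (3.3).

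**Assumptions.** POD#1 lasts 24 h (12 and 16 h also shown), because the documents do not define its length. PCA demand is flat at 1 unit per hour. VR lowers it over T=0-90 by a fraction f relative to the iPad. A share d of the lowered amount is taken later, outside all recorded windows.

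**1. Coverage.**
- All windows: (60 + 30 + 60) × 2 = 300 min. 300/1440 = 20.8% of 24 h; 300/960 = 31.25% of 16 h; 300/720 = 41.7% of 12 h.
- After device start: (30 + 60) × 2 = 180 min. 180/1440 = 12.5%; 180/960 = 18.75%; 180/720 = 25.0%.
- Unrecorded in a 24 h day: 24 − 5 = 19 h.

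**2. Saving against postponement.** Over T=0-90 in both sessions the iPad arm uses 3 units and the VR arm 3(1 − f), so the windowed reduction is f whatever d is. The reduction in the 24 h total is 3f(1 − d)/24.

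| f (shown by T=0-90) | 24 h total, d = 0 | d = 0.5 | d = 1 |
|---|---|---|---|
| 20% | 2.5% | 1.25% | 0% |
| 30% | 3.75% | 1.88% | 0% |
| 50% | 6.25% | 3.12% | 0% |

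The windowed result is the same across each row; only the total differs.

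**3. The afternoon pre-session hour.** Some between-session use is recorded, because the afternoon session has its own T=-60-0 window. Take f = 30% and suppose that all the displaced morning demand, 1.5 × 0.30 = 0.45 units, falls in that hour. The VR arm then shows 1.45 units there against 1.00.
- If that hour is the afternoon baseline, the change in hourly rate in the VR arm is 0.70 − 1.45 = −0.75. Without displacement it is 0.70 − 1.00 = −0.30. The iPad arm shows 0. The VR benefit is exaggerated.
- If all windows are summed, the VR arm shows 1.00 + 1.05 + 1.45 + 1.05 = 4.55 against 5.00, a 9% reduction. With the displaced demand wholly unrecorded it would be 0.9/5 = 18%. Here the window corrects part of the distortion.

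Section 6.3 does not say which handling applies.

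**4. What a total can resolve at this size.** For a between-arm difference relative to the mean, the 95% CI half-width is 2.10 × CV × √(2/10). With an assumed CV of 30% to 60% this is 28% to 56%. A 30% windowed effect with no postponement is 3.75% of a 24 h total, or 0.9/16 = 5.6% of a 16 h total. Neither can be distinguished from 0%.

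**The case against.** The strongest reply is that nothing is hidden. The scope sentence in section 3.1, read with the one after it, mainly excludes use after discharge. A reader might infer that it promises a full-day total that the plan then fails to collect, but the text does not go that far. The endpoint is labelled as peri-session in the synopsis and in sections 4.2, 4.5 and 6.1, and a peri-session measure is legitimate for a peri-session claim. This stands. What remains is that the hypothesis, objective and Aim 2 claim more than the endpoint can show.

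Second, bias needs postponement to differ between arms. Controls also get a 30-minute session, and both arms keep their personal devices. No document figure shows differential deferral. The increase in pain mentioned in section 5.3 has no stated timing, and the first hour after the session is recorded. This also stands: the mechanism is conditional. It is not far-fetched, however, since the trial's own hypothesis is that VR distracts more.

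Third, a full-day total at 10 per arm cannot separate a diluted true effect from none, as step 4 shows. That is correct, and it limits what the fix can deliver. It does not justify leaving the quantity uncollected in a pilot whose stated focus is estimates and confidence intervals.

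**Conclusion.** The concern holds as a mismatch between objective and endpoint. The plan speaks of postoperative opioid consumption but measures PCA use in 300 minutes of POD#1 (20.8% of an assumed 24 h), 180 of them (12.5%) after device start. If VR postpones demand past T=90 more than the iPad does, the T=0-90 comparison would present postponement as reduction. Morning demand that falls in the afternoon pre-session hour is recorded, but would overstate the VR benefit if that hour serves as baseline.

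A reader might go further and infer that deferred demand will be scored as opioid saved, that no use between sessions is counted, or that a particular percentage of false reduction can be expected. The documents support none of these. Differential deferral is unproven, the afternoon T=-60-0 hour is captured, and the percentages in the working rest on assumed demand, f and d. They show the mechanism and do not estimate a bias. This is a worthwhile, low-cost improvement and not a flaw that invalidates the pilot.

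**What to change.** 1. Abstract from the pump or chart record, for each patient, cumulative PCA morphine equivalents from the morning T=0 to a fixed end of POD#1, and record the time of PCA discontinuation. A fixed end keeps the observation period comparable across patients.
2. Report the between-arm difference in this total with its CI beside the T=0-90 result, as a companion estimate.
3. State in section 6.3 how windows and sessions are combined, and whether the afternoon T=-60-0 hour is used as a baseline.
4. Reword sections 2, 2.1 and 6.3 (Aim 2) so that the windowed endpoint supports only a statement about PCA use during and for one hour after the session.

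The cost is one cumulative figure and one time per patient, for at most 24 enrolled patients, with no added patient contact, plus the wording changes. This assumes that the pump or chart holds the cumulative amount, which the documents do not state. The downside is that the total is more variable and dilutes a short effect, so it neither replaces the windowed endpoint nor settles the question at 10 per arm. It also covers PCA opioid only, so even a clear result would not describe all opioid use on POD#1.

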## 3.2 Allocation to Treatment Groups and Blinding (if applicable)

Patients will be randomized to one of two study arms. Each patient will have a private area preoperatively and postoperatively and no information about the other arm of the study will be disclosed, as to keep the study subjects blinded to the study. All study families and subjects will be consented/assented preoperatively, whether by phone in advance or in person on the morning of surgery. Patients will be blinded to the device upon consent for the study with the description of the use of an "electronic device" in the postoperative setting. This is deliberate, as to minimize any chance of bias. We feel that this is necessary due to the popularity and growing public interest in VR.

## 3.3 Study Duration, Enrollment and Number of Subjects

The anticipated duration of the study is 3-4 months, with total enrollment time of up to 13 days for each patient. This enrollment period includes: preoperative screening and consent, as well as the postoperative intervention and data collection (roughly 100 minutes); follow up survey 48-72 hours post op (roughly 10 minutes); and follow up survey 7-10 days postop (roughly 10 minutes). We plan to enroll at most 24 patients for this pilot study, with a final goal of 10 completed participants in each arm.

## 3.4 Study Population

**Inclusion Criteria:** 

- Subjects age 11 17 years of age
- Patients undergoing idiopathic scoliosis surgery on ERAS spine protocol (which includes postoperative PCA)
- No contraindication to using an iPad or VR device

#### **Exclusion Criteria:**

- Patient/caregiver refusal
- Patients with developmental delay
- Patients with seizure disorder
- Non-English-speaking patients

- Patients with daily opioid use ≥ two weeks
- · Patients with uncorrected visual or hearing impairment
- Patients admitted to pediatric intensive care unit on POD#1

#### 4 STUDY PROCEDURES

## 4.1 Screening/Baseline Visit procedures

Baseline anxiety score will be assessed on a self-report form (STAI short form). The patients will be oriented to their study arm and to the VR device if assigned to that arm. The patient will be oriented to the Wong-Baker FACES pain scale. Baseline pain scores will be obtained through the following method: FACES scale (patient reported) and FLACC score (measured by the trained research assistant). Baseline vital signs will be measured and recorded in the preoperative area. All assessment modalities have been used and validated in the pediatric population.

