## Preoperatively:

- Baseline anxiety score (STAI score) will be assessed
- Baseline pain scores will be obtained: FACES scale (patient reported) and FLACC score (measured by the trained research assistant)
- Baseline vitals will be measured
- Patients will be oriented to their respective devices

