## 3 INVESTIGATIONAL PLAN

#### 3.1 Study Design

This will be a randomized controlled pilot study comparing virtual reality to standard electronic use after pediatric idiopathic scoliosis surgery. Patients age 11-17 years old undergoing idiopathic scoliosis surgery will be included. Patients will be randomized to either the virtual reality or control (iPad) group. The randomization-and-concealment feature of REDCap data capture system will be utilized.

Subject eligibility will be verified by the research coordinator through chart review and patient questionnaire prior to enrollment in the study. The patients will be blinded to their study arm until they agree to be part of the study. Participants will be properly oriented to their respective device (VR or iPad) before surgery. While the use of VR may be new to the patients, VR is a very popular, trending and mainstream concept that is not likely to be unfamiliar to patients in the study age group. The patients will have the ability to stop using the VR device at any time if they choose.

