## Study phases are as follows:

Screening/Consent/Baseline: Randomization and consent will be obtained preoperatively. A baseline anxiety score will be assessed on a self-report form (STAI short form). Patients in the VR arm will be oriented to the VR device before surgery. All patients will be oriented to the Wong-Baker FACES pain scale. Baseline pain scores will be obtained through the following method: FACES scale (patient reported) and FLACC score (measured by the trained research assistant). Baseline vital signs will be measured and recorded. The STAI, FACES, and FLACC scoring tools have all been used and previously validated in the pediatric population.

Intervention/Treatment: On postoperative day (POD) #1 in the morning, patients in both groups will be visited by the research assistant. Standardized scripts will be utilized by the research assistant for the entirety of the data collection. Patients in the VR arm will be offered the VR device for up to 30 minutes. Patients in the control arm will be offered an iPad for up to 30 minutes. After a total of 30 minutes maximum, the session will end. Routine data will be collected on pain scores and PCA use as below for both groups. On POD #1 in the afternoon, a research assistant will return for patients in both

groups, for another session of the respective electronic device for up to 30 minutes. If a patient declines to participate, the reason for declining will be asked for and recorded.

In the control arm of the study, the iPad will have a variety of vetted and screened games available. The content on the iPads will include puzzles, games, and movies that have been previously vetted and approved by the Child Life team, separate from this study, and are currently used as standard of care at UNC. The Child Life team is an integral part of pediatric postoperative recovery at UNC.

In the VR arm of the study, there will be selected programs to choose from. All of the content will be pleasant games or exploring programs, avoiding unpleasant and fast-moving settings such as fighting or racing. All of the content will be age appropriate, vetted and screened by the research team for violence or otherwise stressing scenarios, content requiring rapid eye motion or head movement, and content requiring more body movement than what can comfortably be done in a sitting or reclined position.

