#### 12 CONSENT PROCESS

The recruitment and consent process will be done either by phone with electronic consent (e-consent) or in person. A research assistant or member of the research team will be the recruiters for this study.

E-consent will be conducted via RedCap, which has e-consent capability and knowledge tracks, with the ability for participants to give a physical signature and download a copy of the consent for their own reference. A member of the research team will call patients and their guardians 1-3 days prior to surgery and go through the informed consent process by phone, and will share a RedCap link so families can pull up the consent and go through it while on the phone with the researcher. The recruiter will be immediately available to answer questions by staying on the phone while participants complete the consent. The benefit of offering e-consent is to allow a higher enrollment of interested patients, given the significant time restraints on the morning of surgery that can preclude a successful completion of consent. The in person, day-of surgery consent option will still be offered for families who do not have access to a computer or prefer in person consent.

For in person consents on the day of surgery, each subject will have a private room on the day of surgery in the preoperative area. Consent in person will be obtained in the preoperative area, in person and in a private room with closed doors, preventing those not involved with the study from hearing any private information about the study or the subjects.

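### The protocol gives conflicting orders for the preoperative visit and nothing makes disclosure of the arm wait for the baseline scores, so their freedom from the allocation is not guaranteed

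*Combined protocol and SAP*

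**What the plan says.** Four places in the combined protocol and SAP describe the order of the preoperative steps.

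- **Section 4.1 (Screening/Baseline Visit procedures).** The STAI short form comes first. Next: "The patients will be oriented to their study arm and to the VR device if assigned to that arm". Then comes orientation to the FACES scale, and after it: "Baseline pain scores will be obtained through the following method: FACES scale (patient reported) and FLACC score (measured by the trained research assistant").
- **Section 3.1, study phases (Screening/Consent/Baseline).** It opens with "Randomization and consent will be obtained preoperatively", then lists the STAI, VR orientation, FACES orientation and the baseline pain scores.
- **Synopsis, Preoperatively.** STAI, pain scores and vitals come first. The last item is "Patients will be oriented to their respective devices".
- **Synopsis, Study Duration.** The day-of-surgery entry also names the anxiety and pain scores before orientation.

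On blinding and consent, section 3.1 says: "The patients will be blinded to their study arm until they agree to be part of the study". Section 3.2 conceals the type of device at consent, to limit bias, and gives the popularity of VR as the reason. Section 12 lets the research team take consent in a telephone call 1-3 days before the operation; in-person consent on the day of surgery remains available.

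The description of orientation also varies. The synopsis and the opening of section 3.1 orient both arms to their device. The study phases in 3.1 and section 4.1 mention device orientation only for VR.

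**The concern.** A baseline value is useful because the allocation cannot have influenced it. The usual safeguard is to complete the baselines before the arm is revealed, and this protocol does not state it. For FACES and FLACC, two of the four descriptions run the other way.

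Section 3.2 supplies the reason to care: the protocol itself treats knowledge of the device as a source of bias. FACES and the STAI are self-reports, so a patient pleased or disappointed with the assigned device could answer differently. FLACC is an observer score given by a research assistant, and no blinding of that rater is described.

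Section 5.1 says pain and anxiety scores will be compared between arms, and section 6.3 lists the short STAI under Aim 1. The only STAI administration described is the preoperative one. If it were taken after disclosure, a difference between arms could be chance imbalance or a reaction to the allocation, and the data could not separate the two. Baseline pain scores in a balance table, as covariates, or as the reference for a change score would have the same weakness.

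**Working it through.** The plan gives no figure to reproduce: section 6.4 calls the effect size unknown, and no SD or power is stated. The check is first a comparison of the text, then an illustration of scale.

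**1. Order by section**

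| Place | STAI | FACES and FLACC |
|---|---|---|
| 4.1 | before orientation | after orientation |
| 3.1, study phases | before orientation | after orientation |
| Synopsis, Preoperatively | before orientation | before orientation |
| Synopsis, Study Duration | before orientation | before orientation |

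The contradiction concerns FACES and FLACC. The STAI precedes orientation in all four.

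**2. When the arm may become known**

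Section 3.1 ends patient blinding at agreement. Section 12 allows agreement 1-3 days before surgery. No section requires completed baselines before randomisation or disclosure. So disclosure before the STAI is permitted, though no section schedules it.

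**3. Which planned analyses are touched**

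The primary outcomes in section 6.1 are postoperative pain scores and PCA opioid use, compared by two-sample t-test (section 6.3) with no preoperative covariate or change score named. Separate T=0 pain scores are taken on POD#1. Let b be a shift in the preoperative score, in SD units, caused by knowing the arm:

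- raw postoperative t-test: bias = 0
- change from preoperative baseline: bias = -b, so b = 0.5 gives -0.5 SD
- baseline-adjusted contrast: bias = -(slope × b), so b = 0.5 gives -0.10, -0.25 and -0.40 SD at slopes 0.2, 0.5 and 0.8

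The slopes and b are assumptions. The plan names neither of the last two analyses.

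**4. Would a shift be noticed?**

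Input: 10 completed per arm (section 3.3), hence 18 degrees of freedom and t(0.975) = 2.101. The 95% CI half-width for a between-arm baseline difference is 2.101 × √(2/10) = 0.94 SD. Noncentral t, two-sided 5%:

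| Assumed shift | Chance of p < 0.05 |
|---|---|
| 0.3 SD | 9.7% |
| 0.5 SD | 18.5% |
| 0.8 SD | 39.5% |
| 1.0 SD | 56.2% |

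A shift of 0.5 SD would be missed 100 - 18.5 = 81.5% of the time, so a balance table is poor protection.

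**5. The same on the STAI scale (illustration only)**

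The short STAI runs from 6 to 24 (section 5). Assume a 2-point shift and an SD of 3, 4 or 5. SE = SD × √(2/10).

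| SD | SE | Shift / SE | Chance of p < 0.05 |
|---|---|---|---|
| 3 | 1.34 | 1.49 | 29% |
| 4 | 1.79 | 1.12 | 19% |
| 5 | 2.24 | 0.89 | 14% |

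The size of the shift matters as much as the SD. At SD 4, a shift of 1 point gives 8% and one of 3 points gives 36%.

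**The case against.** The strongest reply is that little in the planned analysis depends on these values. The primary comparison is postoperative, uses no preoperative score, and has its own POD#1 starting value. That stands, and it limits the consequence.

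Second, the STAI is listed ahead of orientation everywhere, including in section 4.1, and a randomisation that stays concealed cannot alter a self-report. That also stands. The STAI is exposed only through the open-ended timing of disclosure.

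Third, the 2-point shift has no source in the documents, and the 5% level is nominal, because section 6.3 plans a Bonferroni correction and puts estimates and intervals first. The figures show scale and nothing more.

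Fourth, Aim 1 is worded as a comparison of postoperative scores, while the only STAI described is preoperative. That is a separate inconsistency, which reordering the visit would not cure.

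A reader might also infer more than the text supports:

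- *VR patients try the headset before baseline.* The documents say only that they are oriented to it.
- *Phone-consented families know their arm for days.* This is permitted but not described. Section 3.2 conceals the device at consent, and the synopsis puts orientation on the day of surgery.
- *Allocation precedes consent.* Naming randomisation before consent in one sentence does not establish a sequence, and blinding until agreement is ordinary wording.
- *Recruiters can select patients by the next arm.* Section 3.1 specifies REDCap's randomisation and concealment feature, and nothing gives recruiters the next assignment.

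None of this removes the contradiction over FACES and FLACC or supplies the missing rule.

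**Conclusion.** The concern holds in a limited form. The four descriptions conflict on whether baseline FACES and FLACC come before or after the patient learns the arm, and no rule protects any baseline score from earlier disclosure. The pain scores are exposed by the written order in sections 3.1 and 4.1; the STAI only if the arm is disclosed soon after consent.

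It would be wrong to conclude that the baselines are contaminated. The synopsis order, if followed, avoids the problem, so the finding is that protection is not guaranteed. It would also be wrong to conclude that the primary result is biased: the direct bias in the planned postoperative t-test is zero.

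What is at risk is the between-arm comparison of STAI and baseline pain, and any later baseline-adjusted or change-from-preoperative analysis. If knowing the arm shifted a score by 0.5 SD, an adjusted contrast would move by 0.10 to 0.40 SD over slopes 0.2 to 0.8, and a change score by the full 0.5 SD. Those sizes are assumed throughout. The change is still worth making because it is nearly free and a preoperative score cannot be collected again after surgery.

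**What to change.** State one order, identically, in the synopsis (Preoperatively and Study Duration), the study phases of section 3.1, and section 4.1:

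1. Consent and assent, by phone or in person.
2. On the day of surgery, STAI, FACES (after orientation to the scale), FLACC and vitals, entered in REDCap with a time stamp.
3. REDCap allocation opened only once those fields are complete.
4. Family told the arm, followed by a scripted device orientation in both arms, VR or iPad.

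Add to sections 3.2 and 12 that phone consent triggers neither randomisation nor disclosure. In section 3.1, tie the end of patient blinding to completed baselines instead of to agreement.

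The cost is protocol wording and one REDCap rule holding the allocation until the baseline form is saved. REDCap is already used for randomisation and data capture. The scores and orientation already belong to the 30-minute day-of-surgery contact, so no new assessment is needed. For phone-consented families, allocation simply waits until that contact.
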